### 2.2 Secondary Objectives

# 2.2.1 Key Secondary Objectives

The secondary objective is to determine the rate of clinician-noted inaccuracies or major omissions in postoperative ML report cards.

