#### 4.4 Outcomes

# **4.4.1 Primary Outcome Measures**

The primary outcome will be self-reported handoff effectiveness.

The following survey questions will be asked of postoperative providers:

Did you receive at handoff all the information you needed to safely take care of this patient?

[Yes, No]

Did you receive information from the team giving handoff to explicitly help you manage any potential complications or problems? [Yes, No]

If so, please list what problems / topics were discussed? [Free response]

[If with-intervention phase \* ] Did you look at or discuss the postoperative report card for this patient? [Yes, No]

[If  $^*$  yes] Did the report card contain any information that was notably misleading or incorrect?

[Yes, No]

[If yes, please describe: text box]

[If \* yes] Are there any important pieces of information that the computer should have included in the report card but didn't?

[Yes, No]

[If yes, please describe: text box]

[If \* yes] How much did the ML report change questions asked or information transfer at handoff?

[ Not applicable , Not at all , a little , a fair amount , a great amount ]

[If \* yes] How much effort was accessing the report card? [Very easy, easy, some effort, hard, unable to get to it or had to ask for help]

[If \* yes] Was the information presentation in the report card easy to understand? [Easy, some effort, hard to understand, unable to use or had to ask for help]

[If \* yes] Was the information in the report card relevant?
[a great amount, a fair amount, modestly, mostly not, not at all, not sure]

[If \* yes] Was the information in the report card useful to decision making or helpful to your understanding of the patient?
[a great amount, a fair amount, modestly, mostly not, not at all, not sure]

The following questions will additionally be asked of PACU resident physicians:

Did you participate in handoff for this patient? [Yes, No]

Did you visit this patient's bedside or speak to their nurse before being asked to sign them out? [Yes, No]

Figure 7 illustrates the RedCAP survey for safety questions which will be included throughout the study.

Figure 7: RedCAP Safety Survey

Postoperative Al Risk Report Card	Resize font:  Returning?

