This form is to collect reports of problems with the Al generated risk estimat study PI at [contact] if this doesn't cover your needs. The for does try to link to a patient so that we can figure out what caused the proble appreciate all feedback. The study team will never try to figure out who subn you.	rm doesn't track who you are (it is anonymous) but it em. This is an experiment (IRB: 202103210) and we
This form is to report safety problems with the Al postoperative risk report it does try to link to a patient so that we can determine what happens is approved for HIPAA-protected information.	
This field should auto-populate with a study ID from the link you followed to get here. Otherwise, (1) if you have a QR code with the email me link, and you are at a machine with a barcode scanner, click in the below field and scan the QR code (2) this is a HIPAA-protected portal, you can enter any of the Epic patient IDs and the study team will link it to the correct person.  * must provide value	d46e6e6bb147f7ebdf645e2e9be156172c32897e  Expand
Common problems:	☐ The report card is for the wrong patient ☐ The report card generated on a non-surgical patient ☐ The report card generated too early (preop) ☐ The report card generated too late (not immediately postop) ☐ The risk estimates are too low ☐ The risk estimates are too high ☐ The risk estimates were otherwise confusing ☐ The report card does have / use data that I think it should ☐ The report card has incorrect data ☐ The report card display / formatting was broken
This problem made the report card unsafe  * must provide value	○ Yes ○ No reset
Tell us anything about the problem	
	Expand
If you have comments or suggestions that aren't a problem w	vith the report card, include them here

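### As shown in Figure 7, the only safety-survey box for absent data lacks a negation, so omission reports are ambiguous, chiefly in the education and testing phase

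*Combined protocol and SAP*

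**What the plan says.** Section 2.2.1 makes omissions part of the key secondary objective: "The secondary objective is to determine the rate of clinician-noted inaccuracies or major omissions in postoperative ML report cards". Section 1 likewise says that providers will be surveyed on errors, omissions included, to judge how safe the implementation is.

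Two instruments in section 4.4.1 touch on omissions.

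- **Provider survey.** Providers who report having consulted the card are asked "Are there any important pieces of information that the computer should have included in the report card but didn't". The answer is Yes or No, and a Yes opens a text box.
- **Safety survey (Figure 7).** On its timing the plan says: "Figure 7 illustrates the RedCAP survey for safety questions which will be included throughout the study". Under the label "Common problems" it lists ten boxes. One reads "The report card does have / use data that I think it should" and the next reads "The report card has incorrect data". Below them are a required Yes/No item on whether the problem made the card unsafe and a free-text field, "Tell us anything about the problem".

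Section 4.3.1 says which survey is in use when. In education and testing, the QR code on the card leads to the anonymous problem survey. Further questions are added, by date, for the evaluation phase.

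**The concern.** A box in a list of faults has to state a fault. Nine of the ten do; this one, as written, states that the card contains what it should. A clinician who reads it word for word and has noticed something missing has no box to tick, and one who is content with the data could in principle tick it. The person analysing the form cannot tell from the tick alone which was meant.

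What is at stake is the structured record of omissions on this form. That record matters most before the evaluation starts. In the education phase the team reviews staff comments and concerns to decide whether the intervention or the teaching material needs changing (section 5.4), and the template is expected to change with provider feedback (section 4.3.4). An omission that goes unreported there may carry over into the card that is evaluated.

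**Working it through.** **1. The plan's own figure.** The only number tied to this objective is in section 4.5: for 0 of 150 inaccurate reports, an upper 95% limit of 2.4%. The exact two-sided limit for zero events is 1 − 0.025^(1/n). With n = 150, 1 − 0.025^(1/150) = 0.0243, or 2.4%, so the figure is reproduced. It concerns inaccurate reports and does not depend on the wording of this box. Correcting the box leaves it unchanged, along with the power statement.

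**2. The box against its neighbours.** The ten boxes cover: wrong patient, non-surgical patient, too early, too late, risks too low, risks too high, risks otherwise confusing, the box in question, incorrect data, and broken display. Incorrect data has its own clear box. Absent data has no other.

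**3. What a tick or a blank can mean.**

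| Respondent | Omission present | No omission |
|---|---|---|
| Reads the box as intended | ticks (correct) | blank (correct) |
| Reads the box literally | may leave blank (missed) | may tick (false report) |

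Suppose a fraction *q* of respondents read the box literally and act on that reading. The expected share of true omissions missed by the box is then *q*: nothing if *q* = 0, everything if *q* = 1. The documents give no basis for a value of *q*, so the size of the loss cannot be calculated.

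**4. Can an ambiguous tick be resolved afterwards?** Sometimes. The free text may settle it, and the study ID lets the team re-examine that patient's card. But the form is anonymous, so the respondent cannot be asked. The free-text field is also not marked as required, whereas the study ID and the unsafe item are. An answer of *unsafe* could therefore be attached to a tick whose meaning is unknown.

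**5. Where the box is the only structured omission item.**

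| Phase | Planned size (section 4.2.2) | Figure 7 form | Yes/No omission item |
|---|---|---|---|
| Education and testing | 30 working days, 50 patients | yes | not on the linked survey |
| Evaluation, with-intervention days | 60 of 90 working days | yes | yes |

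This takes the additional evaluation questions named in section 4.3.1 to be those printed in section 4.4.1. Section 4.3.1 places them in an appendix, while section 5.1 says the instruments are in the appendix and above. Section 3 allows further delivery-testing periods, so the first row could recur.

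**The case against.** The strongest reply is that the key secondary objective does not rest on this box. The provider survey has a clear omission question, placed beside the inaccuracy question, with a defined set of respondents. That stands, and it rules out a stronger inference that a reader might draw: that the omission rate in section 2.2.1 cannot be obtained. It can, in the evaluation phase.

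Second, Figure 7 is a voluntary form for reporting problems. It has no denominator, and the plan nowhere says that its ticks will be counted as an omission rate. That also stands, and it means the ticks should not be turned into a rate even after the wording is corrected.

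Third, context points to the intended meaning. The box sits in a list of problems, on a form people open when something has gone wrong, and is followed by questions about the problem. Most respondents may well read it as meant, and a satisfied clinician has little reason to open the form. A reader might infer that the ticks are shown to be unreliable in both directions. The documents support only that this is possible.

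Fourth, the wording comes from a screenshot read by a program, and other lines of that figure are damaged. A lost *not* or *n't* cannot be excluded. Against this, the damage lies mostly at column edges, this item reads as a complete line, and a contracted negative survives elsewhere on the form. This is a reason to check the live form before changing it.

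Finally, section 5.4 provides for staff comments to be recorded directly during education, so omissions can reach the team by another route. The box is the only structured item for them in that phase, not the only channel.

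**Conclusion.** The point holds as a minor instrument error. As shown, the single box for absent data says the opposite of what a problem box must say. Its ticks are ambiguous and its blanks may hide omissions. The consequence is confined to omission reports made in education and testing, and to anyone in the evaluation phase who completes only the anonymous safety form. The main comparison and the evaluation-phase measurement of "the rate of clinician-noted inaccuracies or major omissions in postoperative ML report cards" are unaffected.

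The conclusion rests on two assumptions: that the live form carries the wording shown in the protocol, and that the linked education-phase survey omits the section 4.4.1 questions, as section 4.3.1 indicates.

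**What to change.** 1. Check the live REDCap form. If the negation is already there, correct only the figure in the protocol.
2. If the wording is as shown, insert *not* after *does* in that box and record the date of the change.
3. Treat ticks made before that date as unclassified, unless the accompanying free text makes the meaning clear.
4. State in section 5.3 that the omission rate comes from the Yes/No item in section 4.4.1 only, with providers who answered that item as the denominator. Report Figure 7 ticks descriptively, as spontaneous problem reports, and not as a rate.

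The cost is one word in REDCap, a date stamp, and a sentence or two in the statistical section. No new data collection is needed.

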### 4.4.2 Secondary Outcome Measures

A research assistant will directly observe up to 150 OR - PACU and PACU-Ward handoffs in the intervention phase. An assessment form is attached. After direct observation, the research assistant may ask unstructured clarifying questions and present the survey questions discussed above.

We will conduct 20-30 debriefing interviews with ward and PACU clinicians on their perception of handoff effectiveness and the usefulness of the report card. These will be audio recorded and transcribed.

We will extract exploratory clinical outcomes from the EHR: ICU admission, hospital length of stay, discharge disposition (including death), and changes in serum creatinine (acute kidney injury).

### 4.5 Sample Size

Precision on the absolute rate of clinician-rated inaccurate reports depends on the rate, but for 0/150 clinically inaccurate reports, the upper 95% confidence limit is 2.4%. Handoff surveys will be dichotomized into (un)acceptable. If the baseline rate of "acceptable" handoff is 70%, 50 patients without and 100 patients with intervention implies an 18% absolute increase as the minimum change with 80% power. The study is designed primarily to assess the perceived safety and workflow integration of the report card, not any patient outcomes.

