For each included patient, the ACT clinician will review the report card information, and the postoperative providers will receive it via a print-out or an Epic Best Practices Advisory integrated into their workflow. Our study will include 3 phases: (1) pre-intervention observation of handoff practices, (2) education and workflow adaptation of the intervention, and (3) non-randomized evaluation. During the education and non-randomized evaluation phases, some days will be without-intervention and others with-intervention. On with-intervention days, all eligible patients on a given day will receive the intervention. On without-intervention days no patients will receive the intervention, but handoff outcome measures will be assessed. The main comparison will be between with-intervention and without-intervention days in the evaluation phase. The primary outcome measure we will study is handoff effectiveness in the recovery room or wards. We will also survey providers on any inaccurate items, or major omissions.

This study will be conducted with a waiver of informed consent. It offers non-significant risk to patients. The ML report card will not recommend specific treatments, and decisions will remain in the hands of the supervising physician in all phases of care. The postoperative provider will also be given information about the report card and its limitations.

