### 4.2.2 Durations and sample sizes

The planned duration and size of each phase is

- Pre-intervention observation: 60 working days, 50 patients
- Education and intervention delivery testing: 30 working days, 50 patients
- Intervention evaluation: 90 working days, 350 patients divided into 30 without-intervention days and 60 with intervention days.

The exact number of providers surveyed is difficult to project, because some providers will care for multiple patients, nurses and midlevel providers change their assignments, and staff turnover may occur. We anticipate surveying fewer than 60 distinct PACU RNs, fewer than 15 PACU residents, fewer than 20 PACU physicians, fewer than 60 distinct floor RNs, and fewer than 25 distinct midlevel providers.

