#### 4.3.5 Adherence

Crossover from non-contact to contact will not occur because report cards are not generated for these patients. Our outcome survey will detect if providers believe they used the report, but no other encouragement to use it will be provided. Cross-over into non-contact (failing to contact the correct provider) will be minimized by appropriate training to ACT clinicians.

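### Does section 4.5 base its 2.4% upper limit for inaccurate report cards on a number of cards the trial will not have?

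*Combined protocol and SAP*

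**What the plan says.** The key secondary objective (section 2.2.1) is the "rate of clinician-noted inaccuracies or major omissions in postoperative ML report cards". Section 4.5 gives the only precision statement for it: "for 0/150 clinically inaccurate reports, the upper 95% confidence limit is 2.4" per cent. It does not say where the 150 comes from.

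Three other parts of the plan bear on the number of cards:

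- The power statement for the handoff outcome, also in section 4.5, assumes "50 patients without and 100 patients with intervention".
- Section 4.2.2 plans an evaluation phase of "350 patients divided into 30 without-intervention days and 60 with intervention days", and 50 patients in the education phase.
- Section 4.4.2 allows for at most 150 directly observed handoffs, at which the survey questions may also be put.

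On who has a card to rate, the Non-Technical Summary states: "On without-intervention days no patients will receive the intervention". Section 4.3.5 says of non-contact patients that "report cards are not generated for these patients". In section 4.4.1 the question about misleading or incorrect content follows only from a yes to "Did you look at or discuss the postoperative report card for this patient".

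**The concern.** The figure 150 equals the sum of the 50 and 100 patients in section 4.5's power statement. If that is its source, a third of the denominator consists of patients for whom no card exists and no inaccuracy can be rated. The precision would then be overstated: 100 cards, not 150, would support the limit. Section 4.2.2 points the other way, with more than 200 cards expected.

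The inaccuracy rate is how the plan judges whether the report card is safe to use, and section 4.5 describes the study as designed mainly around perceived safety and workflow. A reader who wants to know how large an inaccuracy rate could be ruled out after a clean result finds one number, and it matches neither of the plan's own counts of patients with the intervention.

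**Working it through.** **Inputs.** 0 of 150, 95%, limit 2.4% (section 4.5); 50 without and 100 with the intervention (section 4.5); 350 patients over 30 and 60 days (section 4.2.2); 50 education-phase patients (section 4.2.2); at most 150 observed handoffs (section 4.4.2).

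**Step 1: reproduce the plan's figure.** With zero events, the exact (Clopper-Pearson) two-sided 95% upper limit is 1 − 0.025^(1/n). For n = 150 this is 2.43%, which agrees with the stated 2.4%. The one-sided exact limit would be 1.98% and the rule of three 2.00%, so the plan used the two-sided exact limit.

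**Step 2: count the cards.**

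- Section 4.5's power statement: 100 patients with the intervention.
- Section 4.2.2: 350 × 60/90 = 233, assuming the same number of patients per day on both kinds of day. If days with the intervention take 60% to 73.3% of patients (an assumption), the count is 350 × 0.60 = 210 to 350 × 0.733 = 257.
- Observed handoffs: 150 × 60/90 = 100 on days with a card, if observation is spread in proportion to days (an assumption; the plan does not say).
- Education phase added to section 4.5's 100: 100 + 50 = 150 if every education patient got a card. The Non-Technical Summary says otherwise: "During the education and non-randomized evaluation phases, some days will be without-intervention and others with-intervention". If those days also ran 2:1 (an assumption), the count is 100 + 50 × 2/3 = 133.

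**Step 3: apply the same formula, zero events.**

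| Rated cards | Upper limit |
|---|---|
| 100 | 3.62% |
| 133 | 2.73% |
| 150 | 2.43% |
| 210 | 1.74% |
| 233 | 1.57% |
| 257 | 1.43% |

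**Step 4: what 150 would need under section 4.2.2.** The share of cards rated would be 150/233 = 64%, or 150/210 = 71% and 150/257 = 58% at the ends of the accrual range. Section 7.3 makes the survey voluntary, so a denominator somewhat below the number of cards issued is to be expected. The 1.6% limit needs every card to be rated, which is less realistic than the stated 2.4%.

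**The case for a change.** The strongest case for a change is that a number under the Sample Size heading should match the planned sample or say what it assumes. Every route to 150 needs something the plan does not state. Adding 50 and 100 counts patients without a card. Section 4.2.2 needs a rating rate that is not given. The observed handoffs are a ceiling on two types of handoff and are not limited to days with a card. The education-phase route needs all 50 patients to have had a card, and section 4.3.1 reserves the additional survey questions for the evaluation phase. Several providers may also respond about one card, so without a stated unit a careless analysis could count surveys as if they were independent cards.

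Much of this stands as description. Section 4.5 does not name the unit, the phase or the rating rate, and its 100 patients with the intervention do not match the roughly 233 implied by section 4.2.2. But that mismatch concerns the power statement for the handoff outcome; the 50 and 100 are not offered there as a count of cards. Nor are all routes to 150 closed: the route through section 4.2.2 is open, at an ordinary rating rate. The point about units is a sound analytic choice. The objective is worded as a rate among report cards, which already points an analyst to one unit per card.

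**Conclusion.** The concern does not call for a change. The 2.4% limit is correct for the case it describes, and section 4.5 puts that case as an illustration, not as a planned count. The documents do not show it to be a precision the design cannot deliver: about 64% of 233 cards gives it, on equal accrual per day and one rating unit per card. Across the counts considered, the zero-event limit runs from 1.4% to 3.6%, and the stated value lies inside that range.

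Nothing in the plan turns on where in that range the trial falls. There is no acceptance threshold, stopping rule or test tied to the inaccuracy rate, and section 6.2 plans no formal interim analysis. The reported interval will use the number of cards actually rated, so the final estimate and its limit are the same whichever planning figure is written down. The missing source of the 150 is a detail that an analyst fills sensibly by reporting the observed denominator and counting each rated card once.

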# Title:

Machine Learning for Postoperative Care

Short Title ODIN-Pilot

Registration: NCT04877535

Version: 3.0; Dec 28 2022

Version 1.10 adds an education and implementation phase between the pre-intervention and post-intervention phases. This will be necessary to give all the participating nurses time to learn where the machine-learning information is located in the Epic environment.

Version 1.11 Clarifies the activities of the education and implementation phase, including the lack of additional consent for notification of the intervention.

Version 2.0 is a major change.

- Parent study (TECTONICS) is closing, remove status as a sub-study.
  - Specify anesthesia-control-tower clinical protocols and equipment instead of TECTONICS protocol
  - b. Remove TECTONICS SMB and DSMB
  - c. Remove TECTONICS data retention
- Remove "short report card" comparator
- Change to inclusion criteria:
  - a. remove "observation unit status" and replace it with "risk of unplanned ICU admission in 85%ile
  - b. add Transplant surgery, Otolaryngology, hepatobiliary surgery to included surgical services
  - c. Remove TECTONICS contact-arm inclusion criterion
  - d. Remove PACU anesthesiologist
  - e. Add previously implicit inclusion criteria: weekdays during business hours
- Modify design from pre- vs post-intervention to pre-intervention plus contemporaneous controls with intervention/no-intervention on alternating days
- Clarify many aspects of intervention screening and mechanics as these have updated
- Rename "run-in phase" to "education and adaptation phase"
- Remove investigator [name] (leaving institution)
- Eliminate secondary outcome measure (handoff checklist)

These changes are based on (1) feedback from existing participants (2) technical issues and time-of-day making the existing recruitment strategy too slow (3) transition of parent RCT to usual clinical operations

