### 4.2.3 Case screening and identification

Patients eligibility is pre-screened automatically, and a researcher or ACT clinician verifies their eligibility. The first two enrollment criteria

- Adults undergoing OR procedures in BJH South campus, including all of "Pod 2", "Pod 3", "Pod 5" and excluding all procedure suites such as Interventional Radiology, Parkview Tower "Pod 1", Center for Advanced Medicine "Pod 4", Labor and Delivery suites
- Surgical service is "Acute and Critical Care Surgery", Otolaryngology, Hepato-biliary Surgery, or Abdominal Transplant Surgery

are taken from the surgical schedule. The third enrollment criteria

- Planned non-IČU disposition ("floor" and "observation unit" collectively "ward" patients). is taken from (1) the procedure schedule request, (2) the anesthesiologist day-of-service anesthesia plan documentation, (3) a predictive model based on the scheduled surgery. Cases with > 75% likelihood of direct ICU admission or outpatient discharge are automatically excluded by the predictive model. The final criterion
  - Calculated risk of unplanned ICU admission in the first 7 postoperative days in the top 10% of historical records.

is calculated using the same model described in 4.3.2

[figure not shown]
Once the server has identified patients as likely eligible, they are marked for review in the ACT

ML dashboard, where final eligibility is confirmed.

During the intervention evaluation (phase 3), each day will be with or without intervention for all eligible patients. These will rotate 2:1 over work days, eg week 1 = (with, with, without, with, with), week 2 = (without, with, with, without, with), week 3 = (with, without, with, without)

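### The 18-point power statement in section 4.5 is not met by a two-sided 5% chi-square test, has no stated alpha, and rests on 150 patients that no text links to the 350 planned

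*Combined protocol and SAP*

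**What the plan says.** Section 4.5 gives two figures in support of the trial's size. The first is power for the dichotomised handoff survey: with 70% acceptable at baseline, "50 patients without and 100 patients with intervention implies an 18% absolute increase as the minimum change with 80% power". The second is precision for the inaccuracy rate: "for 0/150 clinically inaccurate reports, the upper 95% confidence limit is 2.4" per cent.

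Section 4.2.2 gives the planned size of the phase that carries the comparison: "Intervention evaluation: 90 working days, 350 patients divided into 30 without-intervention days and 60 with intervention days". The Non-Technical Summary fixes the contrast: "The main comparison will be between with-intervention and without-intervention days in the evaluation phase". Section 4.2.3 says that "each day will be with or without intervention for all eligible patients", in a 2:1 rotation.

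Section 5.3 names a chi-square test for the rate of acceptable handoffs. It gives no significance level, no sidedness and no statement on continuity correction, and no other section supplies them.

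Three further places bear on the counts. Section 7.3 makes the provider survey optional. Section 4.4.2 allows a research assistant to observe at most 150 handoffs in the intervention phase and to put the survey questions afterwards. Section 4.4.1 asks about misleading or incorrect content only of providers who looked at or discussed the card, and section 4.3.5 adds that "Crossover from non-contact to contact will not occur because report cards are not generated for these patients".

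**The concern.** A power statement should describe the planned comparison under the planned test. This one cannot be checked against either. Without alpha and sidedness, the 18-point figure has no single meaning, and the usual reading of a chi-square test does not return it. The 50 and 100 patients add up to 150, which is 150/350 = 43% of the phase that section 4.2.2 plans, and no response rate, evaluable fraction or subsample is given to explain the difference.

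The safety limit has a related gap. Section 4.5 counts reports, but its own power scenario has only 100 patients with a card, while the planned phase would have about 233. The section calls perceived safety and workflow integration the main purpose of the study, so the denominator matters.

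At stake is whether a reader can tell what difference the trial can detect, how many usable surveys are expected from 350 patients, and which safety bound will apply.

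**Working it through.** **Inputs.** From section 4.5: p0 = 0.70, difference 0.18 (so p1 = 0.88), n0 = 50, n1 = 100, power 80%. From section 5.3: chi-square test. Assumed, because it is not stated: two-sided 5%, with one-sided 5% as the alternative. One independent outcome per patient throughout.

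**Step 1: power at the plan's own counts, two-sided 5%, pooled.**
- Pooled proportion = (50 × 0.70 + 100 × 0.88)/150 = 0.82.
- SE under the null = √[0.82 × 0.18 × (1/50 + 1/100)] = 0.0665.
- SE under the alternative = √[0.70 × 0.30/50 + 0.88 × 0.12/100] = 0.0725.
- z = (0.18 − 1.96 × 0.0665)/0.0725 = 0.684, so power = 75.3%.

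**Step 2: look for the convention that gives 18.** The one-sided unpooled version is z = 0.18/0.0725 − 1.645 = 0.838, so power = 79.9%. All variants:

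| Calculation, 50 vs 100, 70% vs 88% | Power at 18 points | Difference for 80% power |
|---|---|---|
| Two-sided 5%, pooled | 75.3% | 18.9 points |
| Two-sided 5%, chi-square by exact enumeration | 76.6% | 18.6 points |
| Two-sided 5%, chi-square with continuity correction, exact | 68.2% | 20.0 points |
| Two-sided 5%, arcsine | 74.2% | 19.1 points |
| Two-sided 5%, unpooled | 69.9% | 20.0 points |
| One-sided 5%, pooled | 83.5% | 17.2 points |
| One-sided 5%, arcsine | 83.2% | 17.3 points |
| One-sided 5%, continuity-corrected | 77.8% | 18.5 points |
| One-sided 5%, unpooled | 79.9% | 18.0 points |

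Only the last row reproduces the stated figure. A chi-square test is non-directional, so that row is not the test in section 5.3.

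**Step 3: the planned counts.** If accrual follows days, 350 × 30/90 ≈ 117 without and 350 × 60/90 ≈ 233 with intervention. Two-sided 5%, pooled, 70% baseline: 80% power at 13.2 points, and 97.7% power at 18 points. This is a best case, because it assumes a usable survey for every patient and independence between patients. With 60% response (70 against 140) the detectable difference is about 16.5 points. With 43% response it returns to about 18.9.

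**Step 4: the safety limit.** The exact upper limit for 0 events in n reports is 1 − 0.025^(1/n).
- n = 150: 2.43%, which reproduces the plan's 2.4%. A one-sided 95% limit would be 2.0%, so this figure follows the two-sided convention.
- n = 100 (patients with a card in section 4.5's own scenario): 3.6%.
- n = 233 (patients with a card in the planned phase): 1.6%.

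The only route found to 18 points is one-sided, while the safety limit beside it follows a two-sided convention. Neither is stated.

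**The case against.** The strongest reply is that the counts need not conflict. Section 4.2.2 counts patients in a phase, while section 4.5 is a conditional illustration. Planning 350 patients to obtain 150 usable outcomes is sensible when the survey is optional. Section 4.4.2 offers an even closer match: up to 150 observed handoffs, after which the survey may be presented, and 150 split 2:1 is exactly 50 and 100. This stands as a plausible origin. But section 4.5 does not refer to it, handoffs are not patients, and the primary outcome is not restricted to observed handoffs. The counts are unreconciled rather than contradictory.

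It is also fair that 18 points cannot be called wrong, since one convention returns it, and that a pilot need not be formally powered. That leaves the request to state the convention and make the named test agree with it.

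A reader might infer that the 50 without intervention are the pre-intervention group, because section 4.2.2 also lists "Pre-intervention observation: 60 working days, 50 patients", or that the count survives from the earlier design, since the version 2.0 change list says "Modify design from pre- vs post-intervention to pre-intervention plus contemporaneous controls". The documents do not support either. Section 4.5 uses the with/without vocabulary of the evaluation-phase days, its 50:100 matches the current 2:1 rotation, and the change list gives no counts.

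A reader might also infer that the true safety bound is 3.6%. That would follow only if the sponsor had counted 50 patients who have no card. The documents do not say so, and 150 rated reports is feasible from about 233 cards.

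**Conclusion.** The point holds as a minor fault of statement. At an assumed two-sided 5% level, the test in section 5.3 gives about 75% power at 18 points (77% exact), not 80%. It needs about 19 points for 80%: 18.9 pooled, 18.6 exact. The shortfall is about 5 percentage points of power (3 exact), or about one point of detectable difference, and more if a continuity correction is applied. The result rests on the plan's 70% baseline and on one independent outcome per patient.

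The link between 150 and 350 is missing, and the set of reports behind 0/150 is not identified, although 2.4% is correct for 150 rated reports.

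A reader might conclude that the trial is undersized. The documents do not show that: with full response and independent patients, the planned 350 would make the 18-point statement conservative.

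**What to change.** - In section 4.5, state alpha and sidedness, and the expected number of usable surveys in each evaluation-phase group. Add one sentence saying how that number follows from the 350 in section 4.2.2 (expected response, the observed-handoff subsample, or otherwise).
- If 50 and 100 at two-sided 5% are kept, restate the figure as about 19 points at 80% power, or about 75% power at 18 points. If one-sided 5% was intended, say so and name the matching directional test in section 5.3.
- A figure for 117 against 233 (about 13 points) may be added, but only as a best case under full response and independence. It should not replace the headline.
- Define the safety denominator as cards delivered and rated, say whether education-phase cards count, and give the limit that matches (0/100 = 3.6%, 0/150 = 2.4%, 0/233 = 1.6%).

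The cost is a few sentences in sections 4.5 and 4.2.2 and, if one-sided testing is meant, in 5.3. No patients or procedures are added.
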